8.7. Repeat Ablations with PFA

Repeat PVI ablations using PFA are permissible within the 90-day blanking period. Any repeat PVI using the PFA system throughout the study follow-up period should be performed according to the procedural steps in Section 8.4. Note, a repeat ablation after the 90-day blanking period will be considered a primary endpoint failure. Any repeat ablation in the left atrium using a non-study device at any time after the index PFA ablation procedure will be considered a primary endpoint failure.

Subsequent ablations in the right atrium are allowed (e.g., typical atrial flutter ablation) at any time throughout the study follow-up period.

If a repeat left atrial ablation is deemed necessary and performed by the Investigator, the following should be performed:

[figure not shown]
- 
- Review medications
- Adverse event assessment
- Review symptoms suggestive of recurrent AF/AT/AFL
- NIHSS Assessment
 - An NIHSS assessment will be administered to all subjects within 3 days prior to, including day of, repeat ablation procedure.

- The NIHSS will be administered by study site personnel who have been certified to perform the NIHSS assessment and are delegated by their respective site to perform such assessment.
- Discharge procedures will be completed in accordance with Section 8.5.

Repeat ablation procedures will be documented on an electronic case report form (eCRF) and as described in accordance with Section 8.4.6. The subject's procedures and follow-up windows will continue based on the index PFA ablation procedure date.

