12.2.3. Primary Effectiveness Objective

Objective

Demonstrate an acceptable chronic effectiveness of PVI ablation with the PFA System, based on freedom from treatment failure.

Hypotheses

For the paroxysmal AF arm:

Ho: PS \leq 55%

Ha: PS $>$ 55%

For the persistent AF arm:

Ho: PS \leq 40%

Ha: PS $>$ 40%

Where PS is the probability of treatment success at 12 months.

Endpoint Definition

The definition of treatment success and failure differs slightly between the paroxysmal and persistent arms of the Pivotal Phase.

Primary Effectiveness Endpoint for Paroxysmal AF

Treatment success is defined as freedom from treatment failure. The study requires 24-hour Holter monitoring at 6 and 12 months in addition to weekly and symptomatic patient activated ambulatory monitoring transmissions from 3 through 12 months, and 12-lead ECGs at all follow up visits. Treatment failure is defined as any of the following components:

- Acute procedural failure (see definition below)
- Documented AF/AT/AFL on Holter/patient activated ambulatory monitoring/12-lead ECG after the 90-day post-ablation blanking period
- Minimum of 30 seconds on Holter/patient activated ambulatory monitoring or 10 seconds on 12-lead ECG recording
- Note: Documented occurrence and treatment of typical right-sided cavotricuspid isthmus dependent atrial flutter is not considered a failure.
- Any subsequent AF surgery or ablation in the left atrium, except for repeat PVI ablations using PFA within the 90-day blanking period.
- Direct current cardioversion for atrial tachyarrhythmia recurrences after the 90-day blanking period.
- Class I or III antiarrhythmic drug (AAD) use after the 90-day blanking period.

Blanking period is defined as the first 90 days after the index ablation procedure. Recurrences of atrial arrhythmias during the blanking period will not be counted in the determination of the first clinical failure for the primary endpoint. Within the blanking period, recurrent arrhythmias can be managed with antiarrhythmic drugs or cardioversions. Titration of Class I and III antiarrhythmic medications are allowed during the blanking period.

Acute procedural failure is defined as:

- Inability to isolate all accessible targeted pulmonary veins (minimally assessed for entrance block and, where assessable, exit block) during the index procedure
- Ablation using a non-study device to isolate any pulmonary vein

Primary Effectiveness Endpoint for Persistent AF

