Rationale for Performance Criteria (Paroxysmal)

[figure not shown]
Traditionally, the choice of acceptable effectiveness performance criteria for paroxysmal AF with 12-month follow-up data is selected based on the 2017 HRS/EHRA/ECAS Expert Consensus Statement on Catheter and Surgical Ablation of Atrial Fibrillation, which provides recommendations for success rates in clinical trials. The recommendation for evaluating the effectiveness of a treatment for paroxysmal AF is as follows: *"If minimum chronic success rate is selected as an objective effectiveness endpoint for a clinical trial, we recommend that the minimum chronic acceptable success rate for paroxysmal AF at 12-month follow-up is 50%."*³ Medtronic proposes a single-arm, non-randomized paroxysmal AF study is appropriate with performance criteria that is established based on effectiveness rates for currently approved ablation catheters (RF ablation, cryoablation, and VGLB ablation), in addition to the recommendation provided by the 2017 Expert Consensus Statement.

Figure 5 and Table 15 display effectiveness rates observed in current clinical trials studying approved catheter ablation technologies in paroxysmal AF patients. Included are published literature where the search criteria include publications of large multi-centered studies where the therapy was the use of catheter ablation (RF ablation, cryoablation, or VGLB ablation) for a PVI-only approach for paroxysmal AF. The summary includes study results published as manuscripts in peer reviewed medical journals. Varying rates in 12-month effectiveness have been observed. Similarly, variations in definitions of primary effectiveness and variations in arrhythmia monitoring have been utilized. The proposed PULSED AF study design has an aggressive definition of primary paroxysmal AF effectiveness (requiring acute success and disallowing AAD use and reablations) and a more rigorous study design (requiring weekly patient activated ambulatory monitoring through 12 months).

To test a novel catheter ablation technology, under these study design requirements, an OPC of 55% provides a reasonable margin to compare the PFA system against current approved ablation technologies.

Figure 5: Current 12-Month Effectiveness Rates in Approved Catheter Ablation Technologies for Paroxysmal AF

[figure not shown]

Table 15: Summary of Published Literature on Catheter Ablation for Paroxysmal AF

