Reference	Design	Sites	Subjects (Ablation Type)	Subject Monitoring (When/How)	Effectiveness Endpoint Assessment	Acute Procedural Success	6M Effectiveness ^{i,ii}	12M Effectiveness ⁱ
STOP AF PAS P100010/R017 "STOP AF PAS Final Report". ²⁴	prospective, single arm	39	354 cryo	ECG @ 3M, 6M, 12M; 24hr Holter @ 6M; 48hr Holter @ 12M; Symptomatic event recorder for 30 days	AF/AFL/AT > 30s; Intervention for AF	98.0%	89% (85-92)	80% (75-84)
FIRE AND ICE Kuck KH, et al. N Engl J Med. 2016; 374:2235-45. ²⁵	randomized (RF and cryo), noninferiority	16	374 cryo	ECG and 24hr Holter @ 3M, 6M, 12M; Weekly and symptomatic TTM	AF/AFL/AT > 30s; AAD use; Reablation	98.9%	81% (77-85)	65% (60-70)
Squara F, et al. Europace. 2015;17:718-24. ²⁶	Consecutive, non-randomized, ambidirectional (prospective and retrospective)	4	178 cryo	ECG and 24hr Holter @ 1M, 3M, 6M, 9M, 12M; Symptomatic 24hr Holter	AF/AFL/AT >30s	100%	88% (82-92)	82% (76-87)
Schmidt M, et al. Int J Cardiol. 2013;167:114-120. ²⁷	Consecutive patients	3	124 cryo	ECG and 72hr Holter @ 1M, 3M, 6M, 9M, 12M; Symptomatic event recorder	AF or Flutter >30s	100%	86% (79-92)	66% (57-74)
Providencia R, et al. Europace. 2017;19:48-57. ²⁸	Consecutive, prospective, non-randomized	6	393 cryo	ECG and 24hr Holter @ 1M, 3M, 6M, 9M, 12M; Symptomatic ECG and 24hr Holter	Any AF/AT >30s; AAD use	99.0%	89% (85-92)	82% (78-86)
FIRE AND ICE Kuck KH, et al. N Engl J Med. 2016; 374:2235-45. ²⁵	randomized (RF and cryo), noninferiority,	16	376 RF	ECG and 24hr Holter @ 3M, 6M, 12M; Weekly and symptomatic TTM	AF/AFL/AT > 30s; AAD use; Reablation	97.9%	82% (78-86)	64% (59-69)
Squara F, et al. Europace. 2015;17:718-24. ²⁶	Consecutive, non-randomized, ambidirectional (prospective and retrospective)	4	198 RF	ECG and 24hr Holter @ 1M, 3M, 6M, 9M, 12M; Symptomatic 24hr Holter	AF/AFL/AT >30s	100%	89% (84-93)	84% (78-89)
Providencia R, et al. Europace. 2017;19:48-57. ²⁸	Consecutive, prospective, non-randomized	6	467 RF	ECG and 24hr Holter @ 1M, 3M, 6M, 9M, 12M; Symptomatic ECG and 24hr Holter	Any AF/AT >30s; AAD use	97.6%	82% (78-85)	73% (69-77)
HeartLight Dukkipati S, et al. J Am Coll Cardiol. 2015;66:1350-60. ²⁹	Randomized (RF and VGLB), prospective	19	167 VGLB	ECG @ 1M, 3M, 6M, 9M, 12M; 24hr Holter @ 6M, 12M; Symptomatic and weekly TTM	AF >1 min; Atypical/unknown AFL/AT; AAD use	97.7%	75% (68-81)	61% (53-68)
Weighted average (weights based on study sample sizes)							84.5%	73.2%

ⁱ Confidence interval calculated with binomial Fisher's exact method

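### After day 90, right atrial ablation for an endpoint arrhythmia is not itself scored as failure, unlike cardioversion or a new class I/III drug; a subject whose arrhythmia escaped the listed recordings stays a success

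*Combined protocol and SAP*

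**What the plan says.** Section 8.7 places no arrhythmia restriction on later right atrial procedures: "Subsequent ablations in the right atrium are allowed (e.g., typical atrial flutter ablation) at any time throughout the study follow-up period". Typical flutter appears there only as an example. Just above, the same section says, without naming a chamber: "Note, a repeat ablation after the 90-day blanking period will be considered a primary endpoint failure".

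Section 12.2.3 and the synopsis list the failure components, for both arms:

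- Ablation: "Any subsequent AF surgery or ablation in the left atrium, except for repeat PVI ablations using PFA within the 90-day blanking period". Right atrial ablation is not mentioned.
- Cardioversion: "Direct current cardioversion for atrial tachyarrhythmia recurrences after the 90-day blanking period". Section 8.8 adds pharmacological cardioversion.
- Drugs: any class I/III use after day 90 (paroxysmal), or a new drug or a dose above the historic maximum (persistent).
- Arrhythmia: "Documented AF/AT/AFL on Holter/patient activated ambulatory monitoring/12-lead ECG after the 90-day post-ablation blanking period", with the threshold "Minimum of 30 seconds on Holter/patient activated ambulatory monitoring or 10 seconds on 12-lead ECG recording".

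The only arrhythmia exempted, both in its occurrence and in its treatment, is typical cavotricuspid isthmus (CTI) dependent flutter.

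The rationale for the paroxysmal goal calls the endpoint aggressive because of "requiring acute success and disallowing AAD use and reablations". The persistent rationale likewise says re-ablations are disallowed.

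**The concern.** The endpoint has two layers: arrhythmia that is recorded, and interventions that reveal a recurrence whether or not it was recorded. Cardioversion and a new antiarrhythmic drug belong to the second layer. Right atrial ablation for a non-CTI arrhythmia is an intervention of the same kind but is missing from it. Two subjects with the same unrecorded right atrial tachycardia would be scored differently: the one cardioverted fails, the one ablated does not. A successful ablation also makes a later qualifying recording less likely.

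The study is single-arm against fixed goals of 55% and 40%. Failures left unscored raise measured success with no control arm to absorb the error, so the direction is always in the device's favour. In addition, the unqualified sentence in Section 8.7 leaves room for two analysts to classify the same right atrial procedure differently.

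**Working it through.** **Step 1: who can slip through.** Take a subject ablated in the right atrium after day 90, with no left atrial ablation, cardioversion or scored drug use.

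| Rhythm treated | Captured on a qualifying recording after day 90? | Score as written |
|---|---|---|
| Typical CTI flutter | either | Success (stated exemption) |
| AF or other AT/AFL | yes | Failure (arrhythmia component) |
| AF or other AT/AFL | no | Success |

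Only the last row is a gap.

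**Step 2: can the last row occur?** Capture is frequent but not complete:

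- Holter is 24 hours, at 6 and 12 months (Table 7).
- Patient-activated monitoring is handed out at the 3-month visit, whose window is days 91 to 105 (Table 8). Missed transmissions need no deviation report (Section 8.18).
- The 3- and 6-month visits may be done remotely (Section 8.9).
- Table 7 marks no 12-lead ECG under repeat ablation. The assessments listed in Section 8.7 apply to repeat left atrial ablation (one item of that list is not visible).
- A rhythm seen only on intracardiac recordings or outside telemetry is not on a listed modality.

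**Step 3: reproduce the plan's figures.** Inputs from the Section 12.2.3 assumptions:

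- 12- and 6-month success of 68% and 79% (paroxysmal), 54% and 72% (persistent)
- 2% acute failure on day 1, counted inside those totals
- chronic failures uniform on days 91–182 and 184–364
- 5% dropout, uniform on days 1–364

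The analysis is Kaplan-Meier S at day 365 with Greenwood sum V = Σ d/[r(r−d)], where d is failures and r is subjects at risk at each failure time. The lower limit is S^exp(1.96·√V/|ln S|), and the arm passes if this exceeds the goal. The interim rules are redacted, so I used one look.

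- Power: about 91% with 165 paroxysmal subjects and about 91% with 150 persistent subjects, against 90% planned.
- Pass probability at the null (55% with 66% at 6 months; 40% with 58%): 2.0% in each arm, below 2.5% as the plan states.

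**Step 4: size of the gap.** Let x be the share of all subjects whose chronic failure goes unscored by this route. The documents give no value, so x is an assumption. Each chronic failure at the null is re-scored as success with probability x/(1 − S₁₂ − 0.02). The denominator is 1 − 0.55 − 0.02 = 0.43 (paroxysmal) or 1 − 0.40 − 0.02 = 0.58 (persistent). At x = 1% this re-scores 0.01/0.43 = 2.3% or 0.01/0.58 = 1.7% of chronic failures. There were 40,000 simulated trials per cell.

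| x | Subjects (165 / 150) | Pass probability, paroxysmal | Pass probability, persistent |
|---|---|---|---|
| 0 | 0 / 0 | 2.0% | 2.0% |
| 0.25% | 0.4 / 0.4 | 2.5% | 2.3% |
| 0.5% | 0.8 / 0.8 | 2.7% | 2.8% |
| 1% | 1.7 / 1.5 | 3.8% | 3.8% |
| 2% | 3.3 / 3.0 | 6.3% | 6.2% |

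Simulation error is roughly 0.1 percentage point. The null here is defined by the stricter scoring.

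**The case against.** The strongest reply is that the arrhythmia component already does most of the work. Weekly and symptomatic transmissions, two Holters, and 12-lead ECGs at scheduled and unscheduled visits, all read by a core lab, should catch most rhythms that lead to an ablation. To stay a success, a subject needs a non-CTI arrhythmia treated only in the right atrium, no qualifying recording before or after, and no cardioversion or scored drug. This stands, and it is why x should be small. A reader might infer that right atrial rescue of any atrial arrhythmia can never lead to failure. The documents do not support that: what is unscored is the procedure, not the recorded rhythm.

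A second reply is that Section 8.7 does not contradict itself. The unqualified sentence sits under a heading about repeat PFA and follows sentences about repeat pulmonary vein isolation, so its natural reading is repeat PFA. That is reasonable. The wording is ambiguous rather than plainly contradictory, and one clause would settle it.

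A reader might also infer that the endpoint is looser than the studies behind the goals. Tables 15 and 16 do not show this. Of nine rows in Table 15, two list reablation (both arms of one randomized trial), one lists intervention for AF, and six list neither. Three of the four rows in Table 16 list reablation, but two of those three count AF only, whereas this plan also fails AT and AFL. The tables do not say whether reablation there included right atrial procedures.

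Finally, the inflated figures are measured against a stricter endpoint than the one written. Under the plan's own definition, the error rate is unchanged. That also stands.

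**Conclusion.** The gap is real but narrow. After day 90 the endpoint scores cardioversion and new class I/III drug use as interventions but leaves out right atrial ablation for a non-CTI endpoint arrhythmia. The omission matters only when that arrhythmia escaped all three listed recording types, and it can only favour the device.

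Its size is unknown. If about 0.25% of subjects are affected, the pass probability at the null stays within 2.5%. At 0.5% (fewer than one subject per arm on average) it is slightly above, at 1% about 3.8%, and at 2% about 6.3%. These figures rest on an assumed rate, a single look at one-sided 0.025, and the stricter scoring as the reference. The sample sizes of 165 and 150 reproduce, and no stated figure is wrong. This is a cheap improvement to the endpoint wording, not a flaw in the planned test.

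**What to change.** Leave the permission to ablate unchanged and alter only the scoring.

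1. In Section 12.2.3 and the synopsis, for both arms, add a failure component: *right atrial ablation after the 90-day blanking period performed for AF, or for AT/AFL other than typical cavotricuspid isthmus dependent flutter*. This uses the exemption the plan already defines.
2. In Section 8.7, cross-reference that component and reconcile it with the unqualified sentence on repeat ablation after blanking, so that the section says which procedures count.
3. Make sure the indication for any ablation during follow-up is captured on the eCRF. The forms are provided under separate cover, so a suitable field may already exist.

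The cost is one clause in each place and at most one eCRF field. Measured success may be slightly lower.

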8.8. Post-Procedural Cardioversions

Electrically and pharmacologically cardioverting the subject to sinus rhythm is allowed in the 90-day post-procedure blanking period at the discretion of the Investigator. Electrically or pharmacologically cardioverting the subject to sinus rhythm after the 90-day blanking period will be considered a primary endpoint failure.

8.9. Scheduled Follow-up Visits

After receiving notice of a completed index ablation procedure, Medtronic will provide the target dates and windows for each visit to the site. Should a subject miss a visit or the visit fall outside the pre-specified window, a study deviation must be reported and the original follow-up schedule maintained for subsequent visits.

Data analyses include follow-up visits, regardless of whether the visit occurs within the window. Therefore, a late visit is preferred over a missed visit but must be accompanied by a deviation. Follow-up visit windows are listed in Table 8 and are based on days after the index ablation procedure.

Table 8: Follow-up Schedule

Occurrence/ Visit	Window (Calculated days after the ablation procedure)	
	Window Start	Window End
Enrollment/Baseline ¹	-30 days	Day 0
Index PFA System Ablation Procedure	Day 0	Day 0
30 day	30 days	44 days
3 month	91 days	105 days
6 month	183 days	197 days
12 month	365 days	395 days

¹Note: if the time between the consent date and the procedure exceeds 30 days, the subject must be re-evaluated against inclusion and exclusion criteria to ensure they still qualify for the study.

Multiple modes of data collections may be employed to support the collection of required visit data at the 3- and 6-month visits such as: In office patient clinic visit, direct to patient contact (i.e. telephone, email, mail contact, etc.), and remote technology transmissions/uploads.

The following information is required to be collected at the follow-up visits:

8.9.1. Thirty Day Visit

- Review medications
- Adverse event assessment
- Review symptoms suggestive of recurrent AF/AT/AFL
- 12-lead ECG

8.9.2. Three Month Visit

- Review medications
- Adverse event assessment
- Review symptoms suggestive of recurrent AF/AT/AFL
- 12-lead ECG
- Provide the subject with patient activated ambulatory monitoring equipment and provide instructions for weekly and symptomatic transmissions
- Cardiac MRI or CT scan:
- Pilot Phase subjects are required to complete a cardiac MRI or CT scan (whichever technology was used at Baseline) of all PVs or their anomalous equivalents.
- All subjects: only in the case of suspected PV stenosis, is cardiac MRI or CT scan required. It is not required at this visit if it was already completed at an earlier visit where PV stenosis was confirmed.

8.9.3. Six Month Visit

- Review medications
- Adverse event assessment
- Review symptoms suggestive of recurrent AF/AT/AFL
- 12-lead ECG
- Remind subject of instructions on patient activated ambulatory monitoring equipment for weekly and symptomatic transmissions
- Only in the case of suspected PV stenosis, is cardiac MRI or CT scan required. It is not required at this visit if it was already completed at an earlier visit where PV stenosis was confirmed.
- 24h continuous monitoring with Holter
- EQ-5D and AFEQT Questionnaires

8.9.4. Twelve Month Visit

- Review medications
- Adverse event assessment
- Review symptoms suggestive of recurrent AF/AT/AFL
- 12-lead ECG
- Only in the case of suspected PV stenosis, is cardiac MRI or CT scan required. It is not required at this visit if it was already completed at an earlier visit where PV stenosis was confirmed.
- 24h continuous monitoring with Holter
- EQ-5D and AFEQT Questionnaires
- Collect or ensure return of ambulatory monitoring equipment

8.10. Unscheduled Office Visits

An unscheduled visit is defined as any unplanned cardiovascular-related office visit or early study exit at the study site that occurs between CIP required visits. If the subject exits the study early, the site should attempt to complete an unscheduled office visit. The following information is required to be collected at unscheduled follow-up visits:

- Review medications
- Adverse event assessment
- Review symptoms suggestive of recurrent AF/AT/AFL
- 12-lead ECG

8.11. Holter and Patient Activated Ambulatory ECG Monitor Management

Market-released Holters will be distributed by a core lab to sites after activation has occurred. All subjects will wear a Holter in conjunction with their 6- and 12-month office visits. Holters will be sent back to the core lab after they have been worn by the subject. The core lab will be responsible for adjudication of atrial arrhythmias for the primary objective of the study. The core lab will manage maintenance, calibration and tracking of the Holters.

Market-released Patient Activated Ambulatory ECG Monitors will be distributed by a core lab to sites after activation has occurred. All subjects will transmit weekly and symptomatic ECGs following their 3-month office visit. The monitors will be returned to the core lab at the end of the study. The core lab will be responsible for adjudication of atrial arrhythmias for the primary effectiveness objectives of the study. The core lab will manage maintenance, calibration and tracking of the monitors.

8.12. 12-lead Electrocardiograms

All 12-lead ECGs will be sent to the core lab. The core lab will be responsible for adjudication of atrial arrhythmias for the primary objectives of the study. Copies of additional source documents may be requested.

8.13. Assessment of Safety

The Pilot Phase safety objective is based on the data collected as discussed in Sections 4.1 and 12.1.

The Pivotal Phase primary safety objective is based on the Adverse Event data collected. Further information on the collection of Adverse Events is discussed in Section 10.

